## **Purpose of the Study and Background**

**Objective:** The purpose of this study is to characterize basic PK parameters (Cmax, t1/2, AUC) in healthy children to contribute to evidence for the safety of Advantage Arrest, consistent with Guidance for Industry--Exposure--Response Relationships (April 2003).

**Background:** The Sponsor/Investigator conducted a preliminary PK study in six adults (Vasquez et al., 2012) in which 38% diammine silver fluoride (silver diamine fluoride) was applied topically to three teeth in each subject and maximum serum concentration and time to maximum serum concentration were studied over four hours. Mean amount of the agent applied was 7.57 mg. Over the four-hour observation period the mean maximum serum concentrations were 1.86 umol/L for fluoride and 206 nmol/L for silver. These maximums were reached at 3 h and 2.5 h for fluoride and silver, respectively. Fluoride exposure was below the EPA oral reference dose. Silver exposure exceeded the EPA oral reference dose for cumulative daily exposure over a lifetime, but for occasional use was well below concentrations associated with toxicity. Nevertheless, the number of subjects was limited and the follow-up period too short to calculate the AUC. Although diammine silver fluoride is available in many countries, there are no other published PK studies to our knowledge.

The Sponsor/Investigator conducted an additional PK study to further characterize the kinetics of silver and fluoride with sixteen healthy adults (Lin et al., 2019) in which 38% silver diamine fluoride was applied topically to five teeth in each subject (estimated 4-11 milligrams per subject), and maximum serum concentration and time to maximum serum concentration were studied via serum and urine samples over 24 hours. Over the 24-hour observation period, the silver serum peak was .67ng/mL. This maximum was reached at 3 h, and the elimination half-life of silver was estimated to be 46 hours. Baseline fluoride serum levels were between less than 10 through 50ng/mL. The estimated urinary fluoride was 1.29mg, and no silver was recovered in the urine. The study duration was too short to fully capture the pharmacokinetics of silver and return of serum silver to baseline levels. A study duration of 4-7 days with 48, 72, 120, and 168-hour sampling time points is needed.

In both studies, the dose and time to peak serum silver was comparable. Peak serum silver concentrations were higher in the Vasquez et al study which could be due to lack of rinsing post-application. In both studies, there was a 400-fold safety margin in the amount applied compared to the US EPA's lowest allowable effect level for silver exposure at 1g.

There are no published PK studies with children. The investigative team at the University of Washington developed a physiologically-based pharmacokinetic (PBPK) model to predict silver disposition in children, as there are data establishing the safety of fluoride exposure in children in both the anesthesia and dental literature. The predictive performance of the model was assessed by comparing the predicted PK profiles and parameters with the observed data from published rat and human data following intravenous or oral silver administration. The PBPK model was applied to the pediatric population by accounting for developmental physiological changes. From this model, the predicted silver concentrations were within 2-fold of observed blood and tissue silver concentrations in rats and within the 95% confidence interval of observed plasma silver concentrations in healthy human adults. For a given SDF dose, the simulated peak plasma silver concentrations were 5.2-, 4.3-, 2.7-, 1.3-fold higher in children aged 1-2

years, 2-4 years, 5-10 years and 12-17 years, respectively, compared to adults. The half-life of silver was comparable in all ages and plasma and tissue silver concentrations were predicted to return to baseline levels within 10 days after SDF application. Based on the predictions, younger children will have transiently higher silver plasma concentrations than adults, though smaller increases are expected if less SDF is applied.

**Assumptions for Proposed Study:** This is a topical agent where the active ingredients are applied to the teeth and eventually swallowed and may be absorbed through the GI tract or excreted. Minimal amounts are absorbed through the oral mucosa. Serum concentrations of silver and fluoride will be proportional to the dose of silver and fluoride administered topically to the teeth as part of Advantage Arrest.

### **Criteria for Subject Selection**

**Number of subjects:** There will be up to 50 healthy children subjects enrolled in the study with the goal of at least 21 subjects to complete the study.

**Gender of subjects:** The subjects will be approximately half male and half female.

**Age of subjects:** Subjects will be 5-12 years of age.

**Racial and Ethnic Origin:** In a small study it is not possible to fully represent the racial/ethnic distribution of the region or US. The investigator will attempt to recruit a racial/ethnic diverse population.

**Inclusion criteria:** Subjects will be healthy. Healthy status will be determined by self-reported medical history evaluated by the attending clinician. Subjects will have at least one carious lesion.

**Exclusion criteria:** Subjects will be excluded if they have oral mucositis, any ulcerative lesions, or hypersensitivity to silver or fluoride. Subjects with a history of SDF treatment within 3 months will be excluded.

### **Methods and Procedures**

**Design of the Study and Minimization of Bias:** Open label exposure--response study.

**Randomization:** Not applicable.

**Blinding:** Not applicable.

**Baseline procedures:** Once informed consent and assent have been obtained, age, race, gender, and ethnicity information will be collected at baseline along with a brief health history. A brief visual examination will be conducted to note any evidence of inflammatory or ulcerative changes to the gums or other oral tissues. Non-fluoride toothpaste will be used on the day of the baseline appointment through the blood draw period. A blood sample of 6 mL (one tube for serum collection) will be withdrawn at an assigned time point using a fluoride free tube.

**Study intervention:** Advantage Arrest, Aqueous Diamine Silver Fluoride [Ag(NH3)2F], CAS RN 33040-28-7, 38.3% to 43.2% in purified water 5.0 - 5.9% (w/v) fluoride; 24.4 - 28.8% (w/v) silver, Silver Diamine Fluoride.

Teeth will be brushed with a soft toothbrush to remove debris and dried with cotton prior to application. The specific procedure is 5 mg (1 drop) of Advantage Arrest will be dispensed into a plastic dappen dish and all of the material will be applied to the carious lesion/s with an applicator. To calculate the amount of Advantage Arrest applied: the dappen dish with the initial amount of Advantage Arrest dispensed and applicator will be weighed before application and after application. The amount applied will be calculated as the difference in weights before and after application. The amount applied will be recorded. The teeth will remain isolated with cotton rolls for 1 minute and then rinsed with water and high volume evacuation. Subjects will not eat for at least 2 h following application of Advantage Arrest.

**Blood sampling following intervention:** Subjects will have one blood sample of 6 mL withdrawn at an assigned time point: 3 subjects per timepoint at 2, 4, 6, 24, 48, 96 and 168 hrs.

**Blood processing:** Blood samples will be spun in a clinical centrifuge, the serum withdrawn, and then the serum will be frozen for later analysis.

**Sample Analysis:** Serum samples will be analyzed for F by ion chromatography and Ag by ICPMS (Inductively coupled plasma mass spectrometry). Cmax, Tmax, Cmin (last measurable time point), t1/2, and the AUC will be calculated from serum samples.

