**Data Analysis and Monitoring:**

**Subject disposition:** The frequency and reason for subject withdrawal will be summarized.

**Data Analysis and reporting:** The PI and sub-investigators will be responsible for performing all analyses, creating the output for the analyses and disseminating results to the study team. The Principal Investigator and the rest of the study team will then review the results. The Principal Investigator will be responsible for drafting and preparing a final report of the study.

**Data Storage and Confidentiality:** The data will be stored on password protected computers in the UCSF Pediatric Dental Clinic in a password protected room. Only investigative personnel will have access. The data will be available for inspection by regulatory monitors and FDA.

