**Risk-Benefit Assessment**

**Risk Category:** Minimal Risk.

**Potential Risk:** Hypersensitivity to silver or fluoride, changes to intraoral tissues: erythema, gingival inflammation, or soft tissue changes. Advantage Arrest has been

used extensively since clearance as a medical device in 2014 and the Sponsor knows of no adverse effects. The same agent is approved in Canada and Japan and there have no harms reported. There may be bruising at the site of the blood collection.

**Protection Against Risks:** The study will be carried out at UCSF Benioff Children's Hospital in the University of California, San Francisco in Pediatric Dental Clinic and the Clinical and Translational Science Institute by licensed personnel under the Clinical and Translational Science Institute.

**Potential Benefits:** The Advantage Arrest will help slow or arrest their existing carious lesion/s and aid in the prevention of new lesions.

**Alternatives to Participation:** The alternative is to decline participation.

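### The available text schedules no oral examination or symptom question after application, so the local reactions the protocol names as risks could go unrecorded

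*Combined protocol and SAP*

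**What the plan says.** **Purpose.** The Objective is to characterise basic PK parameters in healthy children and, through them, to add to the safety evidence for the product.

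**Before application.** Baseline procedures (Methods and Procedures) collect demographics and a short health history, and add: "A brief visual examination will be conducted to note any evidence of inflammatory or ulcerative changes to the gums or other oral tissues". Criteria for Subject Selection excludes children with oral mucositis or ulcerative lesions.

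**After application.** The intervention text covers weighing the material, isolation, rinsing and a period without eating. Blood sampling following intervention then gives each child one draw: "3 subjects per timepoint at 2, 4, 6, 24, 48, 96 and 168 hrs". Nothing else is scheduled.

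**Reporting.** Apart from the PK parameters, the only summary promised is under Subject disposition: "The frequency and reason for subject withdrawal will be summarized".

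**Risks.** Potential Risk (Risk-Benefit Assessment) lists hypersensitivity to silver or fluoride and "changes to intraoral tissues: erythema, gingival inflammation, or soft tissue changes". It also says: "There may be bruising at the site of the blood collection". Protection Against Risks names the sites and says that the work is done "by licensed personnel under the Clinical and Translational Science Institute". It describes no follow-up check.

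**The concern.** The protocol names specific local risks and looks for inflammatory or ulcerative changes once, before the product is applied. It schedules no second look. Serum concentrations cannot stand in for one, because a silver or fluoride level does not show whether the gums are inflamed or whether a child had a hypersensitivity reaction.

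What is at stake is information that no later analysis can recover. Followed as written, the plan makes no record of a reaction in a child who completes. In a child who leaves early, a reaction appears only if it is given as the reason for withdrawal. A final report that mentions no local reactions would read the same whether none occurred or nobody asked.

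**Working it through.** **1. The plan's own figure.** The sampling schedule has 7 times with 3 children each: 3 × 7 = 21. This matches the completion goal in Criteria for Subject Selection, "up to 50 healthy children subjects enrolled in the study with the goal of at least 21 subjects to complete the study". The goal is a minimum, so 21 is used here as the planned number, not as a cap.

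**2. Scheduled observations, before and after application.**

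| Observation | Before | After |
|---|---|---|
| Visual oral examination | yes (Baseline procedures) | none scheduled |
| Health or symptom query | short health history (Baseline procedures) | none scheduled |
| Blood sample | see note | one per child, 2 to 168 h |
| Withdrawal and its reason | – | summarised (Subject disposition) |

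Note: the Baseline procedures paragraph also describes a 6 mL sample whose timing is given only as an assigned one, so that paragraph is not cleanly confined to the time before application. Nothing in it ties the visual examination to a later visit.

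Planned completers with a scheduled clinical check after application: 0 of 21.

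**3. Named risks against what is measured.**
- Systemic exposure to silver and fluoride: informed by the serum assays.
- Erythema, gingival inflammation, soft tissue changes: no measurement after application.
- Hypersensitivity: no measurement after application.
- Bruising from the draw: no measurement.

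**4. What a check at the existing visit could show.** Each planned completer would be seen once:
- 2, 4 and 6 h: 3 × 3 = 9 children
- 24, 48, 96 and 168 h: 4 × 3 = 12 children

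For zero events in n children, the exact two-sided 95% upper limit is 1 − 0.025^(1/n).
- n = 21: 1 − 0.025^(1/21) = 0.161, or 16.1%
- n = 3 (one time slot): 1 − 0.025^(1/3) = 0.708, or 70.8%

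The chance of seeing at least one event among 21 children is 1 − (1 − p)^21. The documents give no reaction rate, so p is assumed:
- p = 1%: 19%
- p = 5%: 66%
- p = 10%: 89%

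These figures concern findings present or reported at the single visit. They do not describe a fixed risk period.

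**5. Is a comparison available?** Yes. Each child has a baseline examination. Because ulcerative lesions are an exclusion, an ulcer seen later would be new. Gingival inflammation is not listed as an exclusion, so for that finding the recorded baseline result is needed to decide what is new.

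**The case against.** **This is a PK study.** The Objective promises PK parameters, and its contribution to safety evidence runs through exposure, which the plan does measure. It promises no estimate of local tolerability. This stands. A reader might infer that the study fails its safety objective; the documents do not support that. The check proposed here is an improvement, and the PK objective does not depend on it.

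**The expected risk is low.** The Risk-Benefit Assessment classes the study as minimal risk, points to extensive use since clearance in 2014, and says the sponsor knows of no adverse effects. This bears on how serious the gap is. It does not supply data on these children, and the same section still lists the local risks.

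**Adverse events may be handled elsewhere.** Some front matter and the consent pages were not available to this review. A reader might infer that the trial has no adverse-event procedure at all; the available text cannot show that. It shows only that none appears in the methods, analysis or risk sections.

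**The yield is small.** Each child would be seen once, at times from 2 to 168 h. A child seen at 2 h says nothing about 24 h, and a transient reaction may have gone by 168 h. There is no comparator. All of this stands and limits what may be claimed, but a count with a known denominator is still more than no record.

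**Conclusion.** The point holds as a modest gap in data collection. In the available text, 0 of the 21 planned completers have a scheduled oral examination or symptom question after application, while the protocol names local tissue changes and hypersensitivity as risks. Serum levels address systemic exposure only.

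The conclusion rests on two assumptions: that the examination under Baseline procedures takes place before application, and that no unavailable page schedules a later check. Confidence is moderate for the second reason. If such a schedule exists, a cross-reference in Methods and Procedures and in Data Analysis and Monitoring settles the matter.

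A reader might also expect the added check to yield a reaction rate or to show that the product caused a finding. The design supports neither: observation times differ by child, and there is no untreated group.

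**What to change.** **Add to Blood sampling following intervention:** *At the assigned blood-draw visit, before the draw, parent and child are asked about symptoms since application, and the baseline visual examination of the oral tissues is repeated where qualified staff are already present. Treated children who leave before the draw are asked the same question once, unless the family has declined contact.*

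**Add to Data Analysis and Monitoring:** *New tissue changes (denominator: children examined after application) and reported symptoms (denominator: treated children asked) are listed descriptively by time slot, beside the amount applied and the serum concentrations. Treated children not examined or not asked are counted.*

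**Cost and limits:**
- A few minutes per child at a visit already held, one form page, and one contact for each treated child who leaves early.
- The protocol names both the dental clinic and the Clinical and Translational Science Institute and does not say who attends the draw, so some children may be asked but not examined.
- No fixed-period rate can be estimated, events cannot be attributed to the product, and precision is low, as shown above.
- Bruising follows the draw, so a question asked before it does not capture that risk.

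### The child dose is given as 5 mg, equated with one drop, but that equivalence is unverified, the dispensed mass is not checked against a limit before use, and the recorded amount is not said to enter the PK analysis

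*Combined protocol and SAP*

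**What the plan says.** The study intervention text under Methods and Procedures fixes the dose as a mass and a drop count together: "5 mg (1 drop) of Advantage Arrest will be dispensed into a plastic dappen dish and all of the material will be applied". The product strength is given as 24.4-28.8% w/v silver and 5.0-5.9% w/v fluoride. On weighing, "the dappen dish with the initial amount of Advantage Arrest dispensed and applicator will be weighed before application and after application"; the difference is recorded as the amount applied. No empty-dish weight, tolerance, maximum or rule for re-dispensing is stated.

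The Background section gives two adult comparators. For the first study, "Mean amount of the agent applied was 7.57 mg"; for the second, the amount was estimated at 4-11 mg per adult. It then states: "In both studies, there was a 400-fold safety margin in the amount applied", measured against 1 g of silver. For children it predicts a peak silver concentration 2.7 times the adult value at ages 5-10 for the same dose, adding that "smaller increases are expected if less SDF is applied".

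The assumptions paragraph states: "Serum concentrations of silver and fluoride will be proportional to the dose of silver and fluoride administered topically to the teeth". Each child gives one post-dose sample, with three children at each of seven times. The sample analysis paragraph derives Cmax, Tmax, Cmin, half-life and AUC from the serum samples and does not mention the recorded amount.

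**The concern.** Two definitions of the dose sit side by side with nothing to tie them together. If one drop from the actual dispenser is not close to 5 mg, staff who count a drop and staff who aim for 5 mg give different doses, and the text does not say which governs. Five milligrams is a very small drop, so the likely direction of any mismatch is upward.

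Dose matters for two reasons. First, the reassurance carried over from adults depends on the amount applied: both the adult comparators and the silver margin are tied to a quantity. Second, no child contributes more than one post-dose point. The concentration-time curve is assembled across children, so a difference in mean dose between two groups of three would look like a change over time and would feed into Cmax, AUC and half-life.

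**Working it through.** **Status of the stated figure.** That one drop weighs 5 mg can be neither reproduced nor refuted from the documents, because density, drop volume and tip are not given. What follows is unit arithmetic under stated assumptions.

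**Assumed inputs (not in the documents):** density 1.0-1.4 g/mL; surface tension 40-72 mN/m; detachment factor f 0.55-0.75; tip width 1-4 mm.

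**1. Volume of 5 mg.** Mass / density: 5/1.4 = 3.57 to 5/1.0 = 5.0 microlitres.

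**2. Drop mass from a tip of width d.** Tate's law: mass = pi x d x surface tension x f / g. Density does not enter.
- 1 mm, 40 mN/m, f 0.55: 7.0 mg
- 2 mm, 60 mN/m, f 0.65: 25.0 mg
- 4 mm, 72 mN/m, f 0.75: 69.2 mg

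The first and last lines stack extremes. Solved for d, a 5 mg drop needs a tip of 0.29-0.71 mm. An 11 mg drop needs 0.64-1.56 mm, so a tip under about 0.64 mm never gives 11 mg and one over about 1.56 mm always exceeds it. As a cross-check on a different assumption, a drop of 20-50 microlitres weighs 20 x 1.0 = 20 to 50 x 1.4 = 70 mg.

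**3. Silver and the crude margin.** Silver = mass / density x w/v strength. The low end is mass x 0.244/1.4 and the high end mass x 0.288/1.0. Margin = 1000 mg / silver.

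| Applied (mg) | Silver (mg) | Margin (fold) |
|---|---|---|
| 5 (nominal) | 0.87-1.44 | 694-1148 |
| 7.57 (first adult mean) | 1.32-2.18 | 459-758 |
| 11 (top of second adult range) | 1.92-3.17 | 316-522 |
| 69.2 (largest assumed drop) | 12.1-19.9 | 50-83 |

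The protocol's 400-fold corresponds to 1000/400 = 2.5 mg of silver, which fits the adult amounts. For a child it is reached at 2.5/0.288 x 1.0 = 8.7 mg to 2.5/0.244 x 1.4 = 14.3 mg applied, or 1.7 to 2.9 times the nominal 5 mg.

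**4. Comparison with adults.** At 5 mg the dose is inside 4-11 mg and below 7.57 mg. A drop must exceed 11/5 = 2.2 times nominal to pass the largest adult amount cited. By the protocol's own 2.7-fold ratio and its proportionality assumption, 5 mg at age 5-10 corresponds to 2.7 x 5 = 13.5 mg in an adult for peak silver.

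**5. What the weighing shows.** The weight before is dish + applicator + product; the weight after is dish + applicator + residue. The difference gives the applied mass correctly, but only afterwards. The dispensed mass would be the weight before minus the empty weight, and no empty weight is taken.

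**6. Dose noise in the pooled curve.** Under proportionality, the mean at a time point scales with the mean dose of its three children. If applied amounts spread evenly over 4-11 mg (assumed, borrowing the adult range), the dose CV is (7/sqrt 12)/7.5 = 26.9%. For a mean of three it is 26.9/sqrt 3 = 15.6%. By simulation (400,000 draws), the ratio of two time-point means then has a 95% range of 0.64-1.56 from dose alone. With doses held to 5 mg +/-10%, the CV of a three-child mean is 3.3% and the range 0.91-1.10.

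**The case against.** The strongest reply is that the protocol specifies 5 mg, not whatever one drop happens to weigh, and that the product is a cleared commercial device whose dispenser may be described in labelling outside these documents. Tip width, surface tension and detachment factor are all outside assumptions, and a range that starts at 1 mm cannot yield 5 mg under the formula used. This stands: the calculation makes a heavier drop plausible and does not prove one.

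The safety consequence is also limited. The Risk-Benefit Assessment reports extensive use with no known adverse effects. Rinsing and high-volume evacuation mean that the applied mass need not be the swallowed mass. The 8.7 mg bound pairs the strongest silver content with the lowest density; at 1.2 g/mL it is 2.5/0.288 x 1.2 = 10.4 mg.

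On the analysis, dose noise may be modest beside biological variation. With an assumed 50% between-child CV, the CV of a three-child mean is 50/sqrt 3 = 29%, and the 4-11 mg scenario raises it only to 33-34%. These points lower the severity.

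A reader might infer several stronger claims that the documents do not support:
- **That the protocol contains an arithmetic error or overdoses children.** Nothing contradicts 5 mg per drop, and if the dispenser delivers about that amount the dosing concern disappears.
- **That no drop mass and no weighing before application are given.** A nominal drop mass and a gross weighing are both there; what is missing is verification, a tare and a limit.
- **That 11 mg is a protocol limit.** It is a benchmark chosen here from the adult amounts cited, and the first adult study is cited only by its mean.
- **That exposure would be lost.** The applied mass is recorded for each child, so normalisation remains possible.

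**Conclusion.** The concern holds as a matter of dose specification and analysis, at minor to moderate severity.

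On dosing, the equivalence of 5 mg and one drop is unverified, and as written the procedure does not reveal the dispensed mass before the child receives it. If the drop is heavier than nominal, which is plausible under the assumed tip sizes, the adult comparison fails above 11 mg and the 400-fold margin fails somewhere between 8.7 and 14.3 mg. Even the largest assumed drop leaves about a 50-fold margin, so this is a gap in control and not a demonstrated hazard.

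On analysis, the recorded mass has no stated role in the PK parameters. The size of that effect depends on how much the applied amounts actually vary: roughly 3% CV per time-point mean if the dose is held to within 10% of 5 mg, and roughly 16% if it ranges as widely as the adult amounts. This part stands even if the drop averages exactly 5 mg, because the design compares different children across time and assumes concentration follows dose.

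**What to change.** 1. **Dose control.** Before the first child, weigh about ten drops from the actual dispenser and obtain the lot density. State the dose in mg of solution, with the corresponding mg of silver and fluoride and a maximum; correct or drop the reference to one drop. Weigh the empty dish and applicator first, and apply only if the dispensed mass is within the maximum. State the silver margin for children at that maximum. Which amount is intended is for the sponsor to decide.

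2. **Analysis.** Report concentrations, pooled Cmax and AUC both raw and per mg of silver or fluoride actually applied, and use dose-normalised concentrations for the pooled half-life. For fluoride, normalise the rise over baseline where a pre-dose sample exists, since in the second adult study "Baseline fluoride serum levels were between less than 10 through 50ng/mL". Keeping the raw results guards against proportionality failing.

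**Cost.** Brief bench work, one extra weighing per child, a short protocol clarification and a little more analysis. If 5 mg is truly intended, a micropipette may be needed, and 3.6-5 microlitres may limit how many lesions can be covered. If a full drop is intended, the margin stated for children may be less favourable than the adult 400-fold. No extra children or blood samples are needed.
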